8.1.1.1 Adverse Events Grading

All AEs (laboratory and clinical symptoms) will be graded for severity and assessed for relationship to the IP (see definitions below). Adverse events characterized as intermittent require documentation of onset and duration of each episode. The start and stop date of each reported AE will be recorded on the appropriate data collection form and eCRF. Changes in the severity of an AE will be documented to allow an assessment of the duration of the event at each level of intensity.

Severity of Event: Adverse events will be assessed by the Investigator using a protocol-defined grading system (toxicity table included in Section 17.2). For events not included in the protocol-defined grading system, the following guidelines will be used to quantify severity:

- Mild (Grade 1): Events that are transient and may require only minimal or no treatment or therapeutic intervention and do not interfere with the subject's usual activities of daily living.
- Moderate (Grade 2): Events that are alleviated with additional specific therapeutic intervention. The event interferes with usual activities of daily living, causing discomfort but poses no significant or permanent risk of harm to the subject.
- Severe (Grade 3): Events interrupt usual activities of daily living, or significantly affects clinical status, or may require intensive therapeutic intervention. Severe events are usually incapacitating.

Relationship to Investigational Product: The assessment of the AE's relationship to the IP will be done by the licensed study physician indicated on Form FDA 1572 and the assessment will be part of the documentation process. Whether the AE is related or not, is not a factor in determining what is or is not reported in this study. If there is any doubt as to whether a clinical observation is an AE, the event should be reported.

In a clinical trial, the IP must always be suspect. The relationship to the IP will be assessed for AEs using the terms related or not related:

- Related There is a reasonable possibility that the IP caused the AE. Reasonable possibility means that there is evidence to suggest a causal relationship between the IP and the AE.
- Not Related There is not a reasonable possibility that the administration of the IP caused the event.

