8.4 Type and Duration of Follow-up of Subjects after Adverse Events

Adverse events will be assessed and followed from initial recognition of the AE through resolution even if the duration of follow-up goes beyond the final follow-up visit.

Serious AEs will be followed through resolution even if duration of follow-up goes beyond the final follow-up visit.

Resolution of an AE is defined as the return to pretreatment status or stabilization of the condition with the expectation that it will remain chronic.

8.5 Procedures to be Followed in the Event of Abnormal Laboratory Test Values or Abnormal Clinical Findings

Results of laboratory values collected during the conduct of the study will be reviewed by the Investigator or designee within 24 hours of receipt at the clinical site. As this study will be conducted in healthy subjects, assessment of laboratory abnormalities will be performed in accordance with the grading scale provided in Section 17.2, which is adapted from the FDA guideline, "Toxicity Grading Scale for Healthy Adult and Adolescent Volunteers Enrolled in Preventive Vaccine Clinical Trials" (DHHS 2007). The adaptation is applied to account for local laboratory normal values and for compliance with the Clinical Data Interchange Standards Consortium. Any findings meeting Grade 3 criteria must be repeated immediately to rule out spurious values. All abnormal laboratory test values and findings on physical examination will be included in the study data and summarized in the safety analyses as described in Section 10.4.5. Any treatment-emergent AEs that are appropriately graded according to the toxicity scale in Section 17.2 will be captured as AEs in the eCRF.

Abnormal laboratory values occurring during the study will be followed until repeat test results return to normal, stabilize, or a cause is identified. If the laboratory abnormality is identified at the final scheduled visit, the subject will be requested to return for additional testing.

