8.6 Halting Rules

8.6.1 Dose Escalation Halting Criteria

If either of the following criteria is met, escalation to the next planned dose cohort will not proceed until all available study data have been reviewed by the SMC.

- Two or more subjects in the same cohort experience a Grade 2 related AE (laboratory or systemic) that is attributed to the study drug and coded under the same high-level term per the Medical Dictionary for Regulatory Activities coding, throughout the duration of the study.
- Two or more subjects in the same cohort experience a Grade 3 AE (laboratory or systemic) that is coded under the same high-level term per the Medical Dictionary for Regulatory Activities coding, regardless of causality assessment by the Investigator, throughout the duration of the study.

If dose escalation is halted, the study may resume if deemed acceptable by the SMC following review of all available study data.

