17.2 Appendix B. Toxicity Tables

Table 17-1 Toxicity Grading Scales for Clinical Adverse Events and Reactions

Cardiovascular	Mild (Grade 1)	Moderate (Grade 2)	Severe (Grade 3)
Arrhythmia	N/A	Asymptomatic; transient signs; no medical	Recurrent or persistent symptoms; medical
Hemorrhage, Blood Loss*	Estimated blood loss is <100 mL	intervention required Estimated blood loss is ≥100 mL; no transfusion required	intervention required Transfusion required
QTc (Fridericia's correction)	Asymptomatic, QT interval 450 to 479 msec (male) and 460 to 479 msec (female) OR increase in interval <30 msec above baseline	Asymptomatic, QTc interval 480 to 499 msec OR increase in interval 30 to 50 msec above baseline	Asymptomatic, QTc interval ≥500 msec OR increase in interval ≥60 msec above baseline
PR Interval (prolonged)	PR interval 0.21 to 0.25 sec	PR interval >0.25 sec	Type II 2 nd degree AV block OR ventricular pause >3 sec
Respiratory	Mild (Grade 1)	Moderate (Grade 2)	Severe (Grade 3)
Cough	Transient; no treatment	Persistent	Interferes with daily activities
Bronchospasm, Acute	Transient; no treatment; forced expiratory volume 71 to 80% of predicted peak flow	Requires medical intervention; normalizes with bronchodilator; forced expiratory volume 60 to 70% of predicted peak flow	No normalization with bronchodilator; forced expiratory volume <60% of predicted peak flow
Dyspnea	Does not interfere with usual and social activities	Interferes with usual and social activities; no treatment	Prevents daily and usual social activity OR requires treatment
Gastrointestinal	Mild (Grade 1)	Moderate (Grade 2)	Severe (Grade 3)
Nausea	No interference with activity	Some interference with activity	Prevents daily activity
Vomiting	No interference with activity OR 1 to 2 episodes/24 hours	Some interference with activity OR >2 episodes/24 hours	Prevents daily activity OR requires IV hydration OR requires medical intervention
Diarrhea	2 to 3 loose or watery stools OR <400 grams/24 hours	4 to 5 loose or watery stools OR 400 to 800 grams/24 hours	6 or more loose or watery stools OR >800 grams/24 hours OR requires IV hydration OR requires medical intervention
Local Reactions	Mild (Grade 1)	Moderate (Grade 2)	Severe (Grade 3)
Pain	Does not interfere with activity	Repeated use of non-narcotic pain reliever > 24 hours OR interferes with activity	Any use of narcotic pain reliever OR prevents daily activity

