10.4. Electrocardiograms

Single 12-lead ECG recordings will be made at Screening, within 60 minutes prior to the start of the IP infusion; at 1 (\pm 10 minutes), 2, 4, 8, and 24 hours after the start of the IP infusion; and on Days 8, 43, 85, and 120 (or ET). Electrocardiograms will be recorded after the subject has been in the supine position for at least 10 minutes. A single repeat measurement is permitted at Screening for eligibility determination. Measurements of the following intervals will be reported: RR interval, PR interval, QRS width, QT interval, and QTcF. Assessments should include comments on whether the tracings are normal or abnormal; rhythm; presence of arrhythmia or conduction defects; morphology; any evidence of myocardial infarction; or ST-segment, T-wave, and U-wave abnormalities.

Actual values and changes from baseline for numeric ECG data will be summarized by visit and treatment for subjects in the safety population. Key parameters including QTcF and PR interval will be graded based on toxicity grading scale in Appendix 3, and the

toxicity grades will be summarized in a table by visit and treatment for subjects in the safety population.

Shift from baseline in interpretation of ECG results will be summarized by visit and treatment using the frequency count and percentage of subjects in each category.

All ECG data will be presented in a data listing.

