Appendix 3 Toxicity Tables

Cardiovascular	Mild (Grade 1)	Moderate (Grade 2)	Severe (Grade 3)
Arrhythmia	N/A	Asymptomatic; transient signs; no medical intervention required	Recurrent or persistent symptoms; medical intervention required
Hemorrhage, Blood Loss [*]	Estimated blood loss is <100 mL	Estimated blood loss is ≥100 mL; no transfusion required	Transfusion required
QTc (Fridericia's correction)	Asymptomatic, QT interval 450 to 479 msec (male) and 460 to 479 msec (female) OR increase in interval <30 msec above baseline	Asymptomatic, QTc interval 480 to 499 msec OR increase in interval 30 to 50 msec above baseline	Asymptomatic, QTc interval ≥500 msec OR increase in interval ≥60 msec above baseline
PR Interval	PR interval 0.21 to	PR interval >0.25 sec	Type II 2 nd degree AV block
(prolonged)	0.25 sec		OR ventricular pause >3 sec
Respiratory	Mild (Grade 1)	Moderate (Grade 2)	Severe (Grade 3)
Cough	treatment	Persistent	activities
Bronchospasm, Acute	Transient; no treatment; forced expiratory volume 71 to 80% of predicted peak flow	Requires medical intervention; normalizes with bronchodilator; forced expiratory volume 60 to 70% of predicted peak flow	No normalization with bronchodilator; forced expiratory volume <60% of predicted peak flow
Dyspnea	Does not interfere with usual and social activities	Interferes with usual and social activities; no treatment	Prevents daily and usual social activity OR requires treatment
Gastrointestinal	Mild (Grade 1)	Moderate (Grade 2)	Severe (Grade 3)
Nausea	No interference with activity	Some interference with activity	Prevents daily activity
Vomiting	No interference with activity OR 1 to 2 episodes/24 hours	Some interference with activity OR >2 episodes/24 hours	Prevents daily activity OR requires IV hydration OR requires medical intervention
Diarrhea	2 to 3 loose or watery stools OR <400 grams/24 hours	4 to 5 loose or watery stools OR 400 to 800 grams/24 hours	6 or more loose or watery stools OR >800 grams/24 hours OR requires IV hydration OR requires medical intervention
Local Reactions	Mild (Grade 1)	Moderate (Grade 2)	Severe (Grade 3)
Pain	Does not interfere with activity	Repeated use of non-narcotic pain reliever > 24 hours OR interferes with activity	Any use of narcotic pain reliever OR prevents daily activity

Table 17-1	Toxicity Grading Scales for Clinical Adverse Events and Reactions
------------	--

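### The QTcF grading row leaves rises above 50 and below 60 msec without an increase criterion, so the SAP grade table can rank a larger prolongation below a smaller one (minor)

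*Protocol*

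**What the plan says.** The QTc row of protocol Table 17-1 (Section 17.2) grades on two limbs joined by OR: the absolute QTcF and the increase from baseline.

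- Grade 1: 450 to 479 msec (men) or 460 to 479 msec (women), or an increase below 30 msec.
- Grade 2: "Asymptomatic, QTc interval 480 to 499 msec OR increase in interval 30 to 50 msec above baseline".
- Grade 3: "QTc interval ≥500 msec OR increase in interval ≥60 msec above baseline".

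SAP Appendix 3 carries the same Grade 2 limb, "increase in interval 30 to 50 msec above baseline". SAP Section 10.4 puts it to use: "Key parameters including QTcF and PR interval will be graded based on toxicity grading scale in" Appendix 3, with the grades tabulated by visit and treatment. The same section also says "Actual values and changes from baseline for numeric ECG data will be summarized by visit and treatment".

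The protocol table also sets AE severity. Section 8.1.1.1 has a generic scale, but restricts it: "For events not included in the protocol-defined grading system, the following guidelines will be used to quantify severity". Section 8.5 adds: "Any treatment-emergent AEs that are appropriately graded according to the toxicity scale in Section 17.2 will be captured as AEs in the eCRF". Section 8.6.1 holds escalation for review by the safety monitoring committee (SMC) under a rule that begins "Two or more subjects in the same cohort experience a Grade 2 related AE (laboratory or systemic"), with the events attributed to study drug and coded to the same high-level term.

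**The concern.** The Grade 2 increase limb stops at 50 msec and the Grade 3 limb starts at 60. For a rise in between, only the absolute limb can assign a grade. At most eligible baselines that limb gives Grade 1 or nothing, whereas a 30 to 50 msec rise is at least Grade 2 from any baseline. A severity scale should not step down as the abnormality grows, and the documents give no reason for it to do so here.

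What is directly at stake is the QTcF grade table in SAP Section 10.4, in a first-in-human study where ECG parameters are among the primary safety endpoints. Following the SAP literally, a programmer would have to print a misleading grade or invent an unwritten rule. AE severity grading inherits the same inversion.

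**Working it through.** **Inputs.** The cut points are those of Table 17-1. The entry ceilings are QTcF 450 msec (men) and 460 msec (women), from protocol Section 5.1.2. The table does not say how the two limbs combine; I take the higher grade. Values are in whole msec, so the gap is 51 to 59.

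**Step 1: grade of a gap rise, by baseline B.** The absolute value is B + rise. A gap rise is ungraded if this is below 450 (men) or 460 (women), Grade 1 from there to 479, Grade 2 from 480 to 499, and Grade 3 from 500.

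| Rise | No grade, men | No grade, women | Grade 1, men | Grade 1, women | Grade 2, both | Grade 3, both |
|---|---|---|---|---|---|---|
| 51 | B ≤398 | B ≤408 | 399–428 | 409–428 | 429–448 | ≥449 |
| 55 | B ≤394 | B ≤404 | 395–424 | 405–424 | 425–444 | ≥445 |
| 59 | B ≤390 | B ≤400 | 391–420 | 401–420 | 421–440 | ≥441 |

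Examples in a man: 400 to 440 (rise 40) is Grade 2; 400 to 455 (rise 55) is Grade 1; 385 to 440 (rise 55) has no grade.

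**Step 2: extent.**
- Some inversion exists at every baseline up to 428, because 428 + 51 = 479. This is all 89 whole-msec baselines from 340 to 428, in both sexes. There is none from 429.
- Every gap rise is below Grade 2 up to baseline 420 (420 + 59 = 479).
- Every gap rise is ungraded up to 390 in men (390 + 59 = 449) and 400 in women (400 + 59 = 459).

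**Step 3: frequency with no drug effect.** The schedule has 9 post-dose ECGs (1, 2, 4, 8 and 24 hours; Days 8, 43, 85 and 120), so 40 × 9 = 360 readings. The documents give no SD for the change, so I assume 8 to 15 msec and a normal distribution with mean 0. Expected readings in the gap = 360 × P(50.5 < change < 59.5):
- SD 8: 4.9e-8
- SD 10: 7.9e-5
- SD 12: 0.0045
- SD 15: 0.12

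**Step 4: if AV-1 did prolong QTcF.** Take one time point in a 6-subject dose group and an assumed mean rise. Let a, b and d be the probabilities of a rise in 30–50, in 51–59 and below 30.

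Chance that at least one subject falls in the gap = 1 − (1 − b)^6.

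For Section 8.6.1, suppose every such rise is a qualifying related AE and ignore the absolute limb. The decision changes if fewer than two subjects are in 30–50, at least two are in 30–59, and nobody reaches 60 (which would already stop dosing under Section 8.6.3):

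P = [(b + d)^6 − d^6 − 6bd^5] + 6a[(b + d)^5 − d^5].

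Example, mean 30 and SD 15: a = 0.427, b = 0.061, d = 0.487. The first bracket is 0.004 and the second term 0.057, so P = 0.060. The chance of at least one subject in the gap is 0.316.

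| Assumed mean rise | At least one of 6 in gap (SD 8–15) | 8.6.1 decision changes (SD 8–15) |
|---|---|---|
| 20 msec | 0–10% | 0.01–3.9% |
| 30 msec | 3–32% | 0.4–6.0% |
| 40 msec | 42–61% | 0.1–2.7% |

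At means of 30 and 40 msec, two subjects land in 30–50 in 81 to 99.9% of cases, so on these suppositions the rule would be met as written.

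**Step 5: after closing the gap.** With Grade 2 as 30 to <60 msec, every gap rise is Grade 2, or Grade 3 if the absolute value is 500 or more. The grade never falls as the rise grows, at any baseline from 340 to the ceiling.

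**The case against.** The strongest reply is that little depends on the grade label. Actual values, changes from baseline, ECG interpretation shifts and full listings are all reported (SAP Section 10.4), and the Investigator reviews each ECG. ECG results are a named input to the blinded review by the safety review committee (SRC) before escalation, and clinically significant results go to the Sponsor first (Section 8.2.2). The Sponsor can ask the SMC to review any concern (Section 8.7.2). Two 55 msec rises would be seen whatever they were called. Nor do the documents suggest that AV-1 prolongs QTcF: they report no binding to normal human tissue and no adverse effects in rats. All of this stands, and it is why the point is minor.

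Three stronger readings are tempting, and the documents do not support them.

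- **That a gap rise recorded as an AE goes ungraded.** Section 8.1.1.1 requires every AE to be graded, and Table 17-1 has a catch-all row for clinical adverse events in which no interference with activity is Grade 1. A recorded rise would probably be Grade 1, still below a 30 to 50 msec rise. The outcome of no grade belongs to the numeric tabulation in SAP Section 10.4.
- **That the gap seriously weakens the escalation rule.** Section 8.6.1 covers laboratory or systemic events. Table 17-1 files QTc under cardiovascular, and Section 8.6.3 treats QTcF in a separate item. The wording does not settle whether a QTcF rise counts. The 42 to 61% in Step 4 concerns entries in the grade table and should not be read as a failure rate for this rule.
- **That the study halting rule is broken.** Section 8.6.3 states its own thresholds (500 msec or a rise of 60 msec; 480 msec for the two-subject trigger), so the gap does not alter it.

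What survives is the inversion itself. None of these safeguards corrects the grade table.

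**Conclusion.** The row is wrong as written, in both documents. In the SAP Section 10.4 table, a rise above 50 and below 60 msec can rank below a 30 to 50 msec rise at any baseline up to 428 msec, and gets no grade from low baselines. This follows from the cut points alone, taking the higher limb where both apply.

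Severity is minor. Without a drug effect the affected cells would very probably be empty. That conclusion rests on the assumed SD of 8 to 15 msec. An effect on Section 8.6.1 is remote: it needs QTcF rises to be recorded as related AEs and to fall within that rule's scope, and even then the decision changes in about 0.01 to 6% of cases under assumed mean rises of 20 to 40 msec. Those mean rises are illustrations with no basis in the documents.

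**What to change.** In protocol Table 17-1 and SAP Appendix 3, set the Grade 2 increase limb to 30 to <60 msec, leave Grade 3 at 60 or more, and add a sentence that the higher of the two limbs applies.

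The cost is one table cell and one sentence in each document, with no new data, visits or analyses. The protocol change needs IRB approval before use (Section 9.1), so it can travel with the next amendment.

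The two documents should change together. If the SAP is corrected first, the same ECG could be Grade 2 in the SAP table and Grade 1 as an AE. In that case, record the departure in SAP Section 11, which already lists one, and note there that AE grades follow the uncorrected protocol table until it is amended.

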ET	early termination
IP	investigational product
IV	intravenous
MedDRA	Medical Dictionary for Regulatory Activities
РК	pharmacokinetic(s)
PT	preferred term
QTcF	QT interval corrected for heart rate using Fridericia's formula
SAE	serious adverse event
SD	standard deviation
SOC	system organ class
t1/2	apparent terminal half life
TEAE	treatment-emergent adverse event
T _{max}	time to reach maximum observed serum concentration
ULN	upper limit of normal
V_z	volume of distribution during the terminal phase

1. Introduction

This document outlines the statistical methods to be implemented during the analysis of data collected within the scope of AbViro, Protocol AV1-PPD-0005 (A Phase 1a, Double-Blind, Placebo-Controlled, Single Ascending Dose Study to Determine the Safety and Pharmacokinetics of AV-1 in Healthy Male and Female Adult Subjects), Protocol Amendment 2, 07 May 2020.

This is a Phase 1a, first-in-human study with AV-1 and is designed to provide initial safety, pharmacokinetics (PK), and incidence of anti-AV-1 antibody responses data regarding AV-1 to help guide further development of AV-1 as a potential treatment against dengue.

The purpose of this statistical analysis plan is to define the planned statistical analysis of the study data consistent with the study objectives.

2. Objectives

2.1. Primary Objective

The primary objective of this study is to determine the safety of a single intravenous (IV) dose of AV-1 in healthy adult subjects.

2.2. Secondary Objectives

The secondary objectives of this study are as follows:

- To characterize the PK of AV-1 following a single IV dose.
- To evaluate if subjects develop anti-AV-1 antibodies following a single IV dose of AV-1.

3. Investigational Plan

3.1. Overall Study Design and Plan

This is a Phase 1a, first-in-human, single-center, double-blind, randomized, placebo-controlled, sequential-group, single ascending dose study to determine the safety of AV-1 in healthy male and female adult subjects when administered as a single IV infusion. Additionally, the PK and the incidence of anti-AV-1 antibody responses will be studied.

Five sequential cohorts of 8 subjects (6 active and 2 placebo) each (Cohorts 1 to 5) are planned for this study. The starting dose of AV-1 will be 30 mg:

The study will consist of a screening period, check-in, a treatment period, and 8 follow-up visits for each cohort.

Potential subjects will be screened to assess their eligibility to enter the study within 35 days prior to investigational product (IP) administration. Eligible subjects will check in to the clinical site on Day -1 (the day before dosing). In each cohort, subjects will fast overnight (nothing to eat or drink except water) for at least 10 hours before the start of the IP infusion. Subjects will remain fasted for 4 hours after dosing with the IP. Subjects will be randomly assigned to receive AV-1 or placebo as follows:

- Cohort 1: AV-1 30 mg (n = 6) or placebo (n = 2) administered as an IV dose
- Cohort 2: AV-1 90 mg (n = 6) or placebo (n = 2) administered as an IV dose
- Cohort 3: AV-1 250 mg (n = 6) or placebo (n = 2) administered as an IV dose
- Cohort 4: AV-1 500 mg (n = 6) or placebo (n = 2) administered as an IV dose
- Cohort 5: AV-1 1000 mg (n = 6) or placebo (n = 2) administered as an IV dose

Sentinel dosing will be used in each cohort as discussed in Protocol Section 8.2.3. In each cohort, the Investigator will review safety data for the sentinel subjects and notify the Sponsor of intent to proceed with dosing the rest of the cohort with a minimum of 72 hours between dosing of the sentinel subjects and dosing the rest of the cohort. Safety data through Day 8 will be reviewed in a blinded fashion by the Safety Review Committee for each dose cohort before escalating to the next dose cohort. Based on the review of safety data, the Sponsor and the Investigator may choose to repeat a dose level, administer a dose less than the previous dose, escalate to a dose lower than the next planned dose, or prolong the duration of the infusion.

Subjects will be confined to the clinical unit from Day -1 until discharge on Day 5. On Day 5, subjects will be discharged after all protocol-specified assessments have been completed. Subjects will return for 8 follow-up visits on Days 8 (+2), 15 (±2), 22 (±2), 29 (±2), 43 (±3), 57 (±3), 85 (±5), and 120 (±5). Subjects will be asked to attend an early termination (ET) visit if they withdraw or are withdrawn from the study prior to the final follow-up visit on Day 120 (±5).

The planned duration for each cohort (screening to final follow-up visit) is approximately 22 weeks.

Safety, PK, and anti-AV-1 antibody endpoints will be evaluated in the study. Clinical laboratory evaluations, physical examination findings, vital sign measurements, safety 12-lead electrocardiograms (ECGs), incidence and severity of adverse events (AEs), and incidence of serious AEs (SAEs) will be monitored to assess safety as specified in protocol Sections 7 and 8.

